12.1.1 Adverse Events of Special Interest (AESI)

12.2 Slit-Lamp Biomicroscopy Examination

A slit-lamp biomicroscopy examination of the cornea, conjunctiva (palpebral and bulbar), anterior chamber including flare, iris, lens including nuclear, cortical and posterior subcapsular cataract opacity scores, and eyelid/lashes will be performed according to the ocular exam detailed in Section 3.5 of the SAP. The results will be graded as normal, abnormal not clinically significant (NCS) or abnormal clinically significant (CS) with flare scores ranging from 0 to 4+ in whole number increments and lens opacity scores ranging from <1 to >3 in half-point increments.

The results will be summarized using counts and percentages for each dose group and for all subjects for each eye (treated eye and contralateral eye). Tables with percentages will be based on the number of subjects in each dose group with responses. A subject listing of the slit-lamp biomicroscopy parameters will also be produced including the AESIs related to anterior chamber flare and lens opacities.

12.2.1 Anterior Chamber Flare

Anterior chamber flare will be graded according to the SUN Working Group Grading Scheme using a 5-unit scale where 0 = None, 1+ = Faint, 2+ = Moderate (iris and lens details clear), 3+ = Marked (iris and lens details hazy) and 4+ = Intense (fibrin or plastic aqueous). Anterior chamber flare grade at each visit and change from baseline will be tabulated using continuous and discrete summary statistics.

AESI related to anterior chamber flare will include those TEAEs with MedDRA PT of 'Flare', as described in . The onset date of each reported AESI will be compared to dates of slit lamp biomicroscopy results, and exams with dates between the onset date and resolution of the corresponding AESI will be flagged as having led to an AESI report. The incidence of AESI related to lens opacities will be included in the aforementioned discrete summary by visit.

AESIs related to anterior chamber flare will also be summarized with counts and percentages for each dose group and cohort with the definition of the anterior chamber flare related AESI according to Section 13.1.1 of the SAP. AESI related to anterior chamber flare will include those TEAEs with MedDRA PT of 'flare'. In order to establish if results at individual visits resulted in an AESI report or not, the onset date of each reported AESI related to anterior chamber flare will be compared to dates of slit lamp biomicroscopy results, and exams with dates between the onset date and resolution of the corresponding AESI will be flagged as having led to an AESI report.

12.2.2 Lens Opacity Examination

Clinical lens opacities will be graded using the Age-Related Eye Diseases Study (AREDS) protocol and the Clinical Lens Grading System (ARLNS) on a 7-unit scale from <1 to >3 with half unit increments. . Lens nuclear opacity, cortical opacity and PSC opacity and changes from baseline summarized using continuous and discrete descriptive statistics.

AESIs related to lens opacities will also be summarized with counts and percentages for each dose group and cohort with the definition of the lens opacity related AESI according to Section 13.1.1 of the SAP. AESI related to lens opacities will include those TEAEs with MedDRA PT of 'eye opacity'. In order to establish if results at individual visits resulted in an AESI report or not, the onset date of each reported AESI related to lens opacities will be compared to dates of slit lamp biomicroscopy results, and exams with dates between the onset date and resolution of the corresponding AESI will be flagged as having led to an AESI report.

12.3 Posterior Segment/Fundus Examination

A posterior segment/fundus examination of the vitreous, macula, optic nerve, peripheral retina and choroid will be performed at each visit. The results will be graded as normal, abnormal NCS or abnormal CS. Vitreous haze is also assessed with possible scores of 0, 0.5+, 1+, 2+, 3+, or 4+. Cup-to-Disc ratio is also assessed in the Posterior Segment/Fundus Examination on a 0.1 to 1.0 scale in increasing increments of 0.1.

The results will be summarized using counts and percentages for each dose group and for all subjects at each visit for each eye (treated eye and contralateral eye). Percentages will be based on the number of subjects in each dose group with responses. AESI will also be summarized with counts and percentages for each dose group and cohort with the definition of the vitreous haze related AESIs according to Section 12.1.1 of the SAP. A subject listing of the posterior segment/fundus examination parameters will also be produced. Vitreous haze related AESI will include those TEAEs with MedDRA PT of 'vitreous haze'. In order to establish if results at individual visits resulted in an AESI report or not, the onset date of each reported AESI related to lens opacities will be compared to dates of fundus exam results, and exams with dates between the onset date and resolution of the corresponding AESI will be flagged as having led to an AESI report.

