12.4 Intraocular Pressure (IOP)

Intraocular pressure (IOP) will be assessed by tonometry (Goldmann Applanation Tonometer, Tono-pen, Noncontact Tonometer [puff tonometry], or Icare Tonometer [rebound tonometry]) according to the optical exam schedule of Section 3.5 of the SAP. Results will be taken from a single measurement per eye and will be recorded in mmHg.

The IOP values and changes from baseline for each eye (treated eye and contralateral eye) will be summarized using continuous descriptive statistics by visit and eye for each dose group and for all subjects. Baseline IOP is the last measurement prior to the first dose of study drug in the treated eye and may occur on a different date than dosing. The first measure taken immediately post-dose will be included in a change from baseline analysis. A subject listing of IOP will also be produced include IOP related AESIs. Tables will also include AESI for each visit with counts and percentages for each dose

group and cohort with the definition for the IOP related AESI according to Section 13.1.1 of the SAP. IOP related AESI will include those TEAEs with MedDRA PT of 'intraocular pressure increased'. In order to establish if results at individual visits resulted in an AESI report or not, the onset date of each reported AESI related to IOP will be compared to dates of IOP assessments, and assessments with dates between the onset date and resolution of the corresponding AESI will be flagged as having led to an AESI report.

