14.1 Visual Acuity (BCVA) with ETDRS and BVRT

The logarithm of the minimum angle of resolution (logMAR) visual acuity is assessed using an EDTRS chart according to Section 3.5 of this SAP. Light perception (LP), detection of hand movement (HM) and ability to count fingers (CF) are also acceptable measures of visual acuity for this study. The Berkeley Rudimentary Vision Test (BVRT) will also be used to assess subjects' visual acuity. Since BCVA is an efficacy endpoint but also a safety output, this analysis will be produced primarily for the Efficacy Evaluable Population, and only repeated for the Safety Population if the Safety Population is different than the Efficacy Evaluable Population.

The observed value and change from baseline visual acuity will be summarized for each eye (treated eye and contralateral eye) for BCVA using continuous descriptive statistics on the logMAR scale by visit for each dose group and for all subjects. If there is no logMAR evaluation available from the EDTRS chart or BVRT assessment, visual acuity measures of LP, HM, and CF will be summarized using the following logMAR equivalents (refer to Section 21 Appendix 1 for full table):

- Light Perception = 4.0 logMAR
- Hand Movement = 3.0 logMAR
- Count Fingers = 2.0 logMAR

BVRT will be summarized in a similar manner as described for BCVA via ETDRS, with discrete summary statistics for frequency of Light Perception, Black White Discrimination, White Field Projection, and Cord Pair. The BVRT logMAR value will be summarized with continuous descriptive statistics. For BVRT, if the Light Perception question is not answered on the eCRF, then values will be imputed from the corresponding Best Corrected Visual Acuity (BCVA) Light Perception answer.

BCVA related AEs of special interest (AESI) will also be summarized with counts and percentages for each dose group and cohort with the definition of the BCVA related AESI according to Section 13.1.1 of the SAP. BCVA related AESI will include those TEAEs with MedDRA PTs of 'visual acuity reduced' or 'blindness'. In order to establish if results at individual visits resulted in an AESI report or not, the onset date of each reported AESI related to BCVA will be compared to dates of BCVA assessments, and assessments with dates between the onset date and resolution of the corresponding AESI will be flagged as having led to an AESI report.

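### SAP 12.3 flags fundus examinations by the dates of lens-opacity AESIs, although the AESI it defines for that examination is vitreous haze; a related sentence in 12.2.1 has an unclear referent

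*SAP*

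**What the plan says.** Section 12.3 of the SAP covers the posterior segment and fundus examination, including the vitreous haze score. It asks for AESI counts and percentages by dose group and cohort for vitreous haze and gives the selection rule: "Vitreous haze related AESI will include those TEAEs with MedDRA PT of 'vitreous haze". The next sentence sets the rule for deciding which examinations led to an AESI report: "the onset date of each reported AESI related to lens opacities will be compared to dates of fundus exam results". Examinations dated between onset and resolution of that AESI are then flagged.

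Section 12.2.2, on lens opacity, selects its AESIs by the preferred term eye opacity and links them to a different examination: "the onset date of each reported AESI related to lens opacities will be compared to dates of slit lamp biomicroscopy results".

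Section 12.2.1, on anterior chamber flare, describes its table as follows: "Anterior chamber flare grade at each visit and change from baseline will be tabulated using continuous and discrete summary statistics". After defining and flagging flare AESIs, it adds: "The incidence of AESI related to lens opacities will be included in the aforementioned discrete summary by visit".

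**The concern.** The flag exists to show whether the result at a given visit went with a reported AESI. In 12.3 the event that is selected (vitreous haze) and the event whose dates drive the flag (lens opacity) are not the same, so the rule as written cannot do this for haze. No other visible rule in the SAP links haze AESIs to individual examinations. The protocol's ophthalmic examination (section 8.8) uses the haze scale to grade inflammation in the vitreous, and safety is the primary objective. A reader of the visit-level fundus output would therefore expect the flag to mark haze events.

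The 12.2.1 sentence raises a smaller question of the same kind. It stands in the flare section, names lens opacities, and refers back to a table without saying which one.

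**Working it through.** No arithmetic on trial data applies, and the plan gives no figure to reproduce. The check compares the rules side by side.

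**Step 1. Date-linking rules by section.** Five SAP sections link AESI dates to examinations. The SD-OCT and NIRAF sections (14.6 and 14.7) rely on the imaging reader's determination instead, so they are not counted.

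| SAP section | AESI selected (preferred term) | Event whose dates are used | Examination flagged | Match |
|---|---|---|---|---|
| 12.2.1 | flare | anterior chamber flare | slit lamp | yes |
| 12.2.2 | eye opacity | lens opacities | slit lamp | yes |
| 12.3 | vitreous haze | lens opacities | fundus | **no** |
| 12.4 | intraocular pressure increased | IOP | IOP | yes |
| 14.1 | visual acuity reduced, or blindness | BCVA | BCVA | yes |

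The matching rules read: flare, "the onset date of each reported AESI related to anterior chamber flare will be compared to dates of slit lamp biomicroscopy results"; IOP, "the onset date of each reported AESI related to IOP will be compared to dates of IOP assessments"; BCVA, "the onset date of each reported AESI related to BCVA will be compared to dates of BCVA assessments"; lens, as quoted above. One section of five is mismatched. Section 12.2.1 holds two linking sentences, one of which names no specific event, so counted by sentence it is one of six. The 12.3 clause equals the 12.2.2 clause except for the examination named, which suggests that the sentence was carried over and only half adapted.

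**Step 2. What the 12.3 rule does to one fundus examination.**

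| Haze AESI ongoing | Lens-opacity AESI ongoing | Flag as written | Flag for haze |
|---|---|---|---|
| yes | yes | yes | yes |
| yes | no | no | yes |
| no | yes | yes | no |
| no | no | no | no |

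The two differ when exactly one of the events is ongoing: a missed flag in the second row and a false flag in the third. This shows how the rule goes wrong, not how often. The frequency depends on AESI counts and dates, which the documents do not give.

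**Step 3. What is not touched.** The haze AESI counts in 12.3 use the preferred term vitreous haze and do not depend on the linking sentence. The ocular TEAE summaries in 12.1 are built by system organ class and preferred term. The primary endpoint, frequency and severity of ocular AEs, comes from those summaries.

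**Step 4. The 12.2.1 sentence.** There are two candidates for the summary it refers to.

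- *The flare-grade table.* It is the nearest antecedent and the only table in 12.2.1 described before the sentence. It is given by visit and with discrete statistics, so both words of the back-reference fit.
- *The general slit-lamp summary in 12.2.* It uses counts and percentages, which SAP 7.4 treats as the summary for discrete variables. Section 12.2 also covers flare and lens opacity scores together and puts both kinds of AESI in one listing. But its summary is not described as by visit.

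The first candidate fits better; the second cannot be excluded.

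**The case against.** The strongest reply is that 12.3 contains a wording slip whose intent is plain. The sentence just before it names vitreous haze, the counts in the same paragraph use the haze definition, and four parallel sections show the pattern. A careful programmer would see what is meant. The consequence is also small: SAP 7.6 refers to 11 subjects, fundus parameters and TEAEs are listed by subject, and a reader could match haze events to examinations by hand.

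Most of this stands and is why the point is minor. It does not remove it. The linking sentence is an operative rule in current text with no redaction in it, and following it gives wrong flags. SAP 17.1 says the revision was meant to bring the text into line with outputs already produced, so the wording cannot simply be assumed to differ from the programs.

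The objection carries more weight for 12.2.1. Because of the second candidate in step 4, a reader might infer that the flare table will certainly carry lens events, but the text does not settle that. A reader might also infer that by-visit flare AESI incidence was never planned. The AESI definitions in 12.1.1 are absent from the public text and 12.2.1 itself has a gap, so that absence proves little.

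**Conclusion.** The 12.3 linking rule is wrong as written and should be corrected: it flags fundus examinations by the wrong event. Confidence is high, since the conclusion rests only on adjacent sentences of current SAP text and on four consistent parallel sections. The severity is minor, because the effect is confined to descriptive visit-level AESI flags.

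The 12.2.1 sentence is an unclear cross-reference, held with lower confidence. If it does mean the flare-grade table, the effect is limited to the by-visit AESI rows there.

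Three stronger readings are not supported:

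- That vitreous-haze AESI counts, the ocular TEAE tables or the primary endpoint are wrong. These are defined by preferred term and do not use the flag.
- That half of the fundus examinations would be misflagged. The two differing rows in the table are logical combinations without frequencies, not an error rate.
- That the outputs already produced are wrong. The visible text does not show which rule the programs used.

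**What to change.** **Section 12.3.** In the linking sentence, replace *lens opacities* with *vitreous haze*.

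**Section 12.2.1.** The sponsor should confirm which event and which table the by-visit incidence sentence means. Then either change the event to *anterior chamber flare*, or move the sentence to 12.2.2 and name the table there.

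**Programs.** Check that the visit-level flags and by-visit AESI rows follow the corrected rules, and re-run them only if they followed the current wording.

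The cost is one phrase in 12.3, one clarified sentence in 12.2.1 and one program check. No new data are needed.

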12.4 Intraocular Pressure (IOP)

Intraocular pressure (IOP) will be assessed by tonometry (Goldmann Applanation Tonometer, Tono-pen, Noncontact Tonometer [puff tonometry], or Icare Tonometer [rebound tonometry]) according to the optical exam schedule of Section 3.5 of the SAP. Results will be taken from a single measurement per eye and will be recorded in mmHg.

The IOP values and changes from baseline for each eye (treated eye and contralateral eye) will be summarized using continuous descriptive statistics by visit and eye for each dose group and for all subjects. Baseline IOP is the last measurement prior to the first dose of study drug in the treated eye and may occur on a different date than dosing. The first measure taken immediately post-dose will be included in a change from baseline analysis. A subject listing of IOP will also be produced include IOP related AESIs. Tables will also include AESI for each visit with counts and percentages for each dose

group and cohort with the definition for the IOP related AESI according to Section 13.1.1 of the SAP. IOP related AESI will include those TEAEs with MedDRA PT of 'intraocular pressure increased'. In order to establish if results at individual visits resulted in an AESI report or not, the onset date of each reported AESI related to IOP will be compared to dates of IOP assessments, and assessments with dates between the onset date and resolution of the corresponding AESI will be flagged as having led to an AESI report.

12.5 Physical Examination

The physical examination results, graded as normal or abnormal NCS or abnormal CS, will be summarized by dose group and for all subjects using counts and percentages (including a summary of baseline values). A subject listing of the physical examination results will also be produced.

12.6 Vital Signs

Vital signs, including pulse, blood pressure, height, weight and temperature, will be summarized with continuous descriptive statistics at each day (including a summary of baseline values) by dose group and for all subjects. Change from baseline will also be summarized to each post-baseline visit. A subject listing of the vital signs results will also be produced.

12.7 Electrocardiogram (ECG)

Heart rate (HR), PR, QRS, QT, and QTc with correction specified as either Bazett or Fridericia, intervals will be summarized using descriptive statistics by dose group and for all subjects at each visit the assessment is taken. Change from baseline to each post-baseline visit and time point will be also summarized. A subject listing of the ECG results will also be produced.

12.8 Clinical Laboratory Data

Clinical laboratory data including hematology, coagulation, serum chemistry and urinalysis are collected at specified visits. Other lab tests which are collected and will be summarized include Complement C4 NEPH, C-reactive protein (CRP), complement total, and erythrocyte sedimentation rate. The quantitative variables will be summarized by dose group and for all subjects with continuous descriptive statistics at each visit and time point where appropriate. The qualitative variables (counts and percentages) will be summarized by dose group and for all subjects at each visit and time point where appropriate. Change from baseline will also be summarized by dose group and for all subjects.

13. Pharmacokinetic Analyses

Pharmacokinetic (PK) analyses will be primarily performed on the PK population with observed data only. To determine the PK profile of IVT injections at the different dose levels of QR-110, the following PK parameters will be calculated if sufficient data are available for each dose:

- $AUC_{0-\infty}$: Area under the curve to infinity will be calculated based on the last observed concentration ($C_{last(obs)}$) using formula: $AUC_{0-\infty} = AUC_{last} + C_{last(obs)} / \lambda z$, if feasible.
- $AUC_{0-t_{last}}$: Area under the curve to the final sample with a concentration greater than lower limit of quantification (LLOQ) will be calculated based on the last observed concentration using the linear trapezoidal method.
- C_{max} , C_0 : The maximum and minimum serum concentrations will be taken directly from the data.
- T_{max} : Time to C_{max} will be taken directly from the data.
- $T_{1/2}$ (if measurable serum levels are obtained): The terminal elimination half-life will be estimated by non-linear regression analysis of the terminal elimination slope, if feasible.
- CL : Serum clearance level will be estimated using the formula: $CL = Dose / AUC_{0-\infty}$.
- V_d (if measurable serum levels are obtained and an elimination rate constant (λz) is estimable): Apparent volume of distribution at steady state of the drug will be determined from trough levels.

Serum concentration below LLOQ prior to dose for the assay will be set to zero for the PK analysis. For other cases concentrations below LLOQ will be set to one half of LLOQ.

All samples obtained from all cohorts will be analyzed to avoid bias in data presentation.

Sparse sampling analysis may be used to mitigate the risk of insufficient data to create individual profiles.

Drug concentrations will be summarized by nominal time point if 3 or more values are available.

Descriptive statistics for PK parameters will be performed if $\geq 50\%$ of subjects have evaluable data and number of values to summarize is ≥ 3 .

Geometric means and coefficients of variation will be tabulated for C_{max} , C_0 , $AUC_{0-t_{last}}$, $AUC_{0-\infty}$, CL , and V_d for each dose group if possible. T_{max} will be summarized by median, minimum and maximum. Mean, standard deviation, minimum and maximum will be provided for $T_{1/2}$.

14. Efficacy Analyses

The Efficacy Evaluable population will be used for the efficacy analyses including mobility course, BCVA, FST, OCI, PLR and VFQ-25/CVAQC. Ocular imaging endpoints will also be summarized with the Efficacy population for all imaging endpoints including ERG imaging, SD-OCT (Photoreceptor Outer Segment Thickness, Full Retinal Thickness, ONL Thickness, Macular Edema), and NIRAF imaging. Selected efficacy endpoints which also constitute a safety outcome may be rerun using the Safety Population if the Efficacy Evaluable and Safety Populations differ. Tables will summarize endpoints using continuous or categorical descriptive statistics by visit and time point where appropriate. Change from baseline visit will be calculated as follow-up visit minus baseline visit. Tables will include sections for adults, pediatrics and combined cohorts according to dose groups.

Subject listings by visit, time point (when applicable) and eye will also be produced.

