## **2.4     Route of Administration, Dosage, Dosage Regimen and Treatment Period**

Intravitreal injection is a well-established route of administration within ophthalmic indications. Systemic exposure to drugs administered via IVT injection is generally low and the technique enables targeting of the product to the intraocular tissues of the eye ([AAO 2015](#)). Intravitreal injection is used in several products for the chronic treatment of ophthalmic diseases (eg, Lucentis®, Eylea™, Macugen®) and the risk of complications is low when injections are performed by trained ophthalmologists ([AAO 2015](#)).

Since IVT injections themselves carry a low risk of serious complications, independent of the product administered, dose levels to be investigated in the study are calculated to be pharmacologically efficacious doses. Evaluation of up to 3 dose levels of QR-110 is planned. Inclusion of up to 3 dose levels enables investigation of a potential dose response relationship for QR-110. Based on the chemistry of the molecule, PK data from toxicology studies, and what is known of other oligonucleotides approved for IVT injection (Macugen®, Vitravene®), systemic absorption is anticipated to be low.

Each subject will receive up to 4 doses of QR-110 at 3 month intervals and will be monitored for 3 months following their last dose of study drug. The dosing interval of 3 months and the 12-month duration of dosing is expected to be in the efficacious range for QR-110.

Administration of 4 doses has been selected to enable evaluation of the safety of repeat dosing of QR-110 and to evaluate potential efficacy parameters. The multiple dose design provides subjects with the potential opportunity for efficacy. A single dose design is not considered acceptable in this population because subjects would be exposed to the risks associated with IVT injection without the possibility of being able to derive any (sustained) benefit. To ensure subject safety in this multiple dose design, an independent Data Monitoring Committee (DMC) will review all available safety data prior to each dose escalation, prior to inclusion of pediatric subjects, and prior to the first subject receiving each subsequent dose of QR-110 (doses 2, 3, and 4). Therefore, the study consists of a single initial dose, with DMC review of cumulative study data and a positive DMC recommendation prior to continuing to each subsequent dose.

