## **10.7 Pharmacokinetics Analyses**

To determine the PK profile of IVT injections at the different dose levels of QR-110, the following PK parameters will be calculated if sufficient data are available for each dose:

- $AUC_{0-\infty}$ : Area under the curve to infinity will be calculated based on the last observed concentration ( $C_{last}(obs)$ ) using formula:  $AUC_{0-\infty}=AUC_{last}+C_{last}(obs)/\lambda z$ , if feasible.
- $AUC_{0-t_{last}}$ : Area under the curve to the final sample with a concentration greater than lower limit of quantification (LLOQ) will be calculated based on the last observed concentration using the linear trapezoidal method.
- $C_{max}$ ,  $C_0$ : The maximum and minimum serum concentrations will be taken directly from the data.
- $T_{max}$ : Time to  $C_{max}$  will be taken directly from the data.

- $T_{1/2}$  (if measurable serum levels are obtained): The terminal elimination half-life will be estimated by non-linear regression analysis of the terminal elimination slope, if feasible.
- CL: Serum clearance will be estimated using the formula:  $CL = \text{Dose}/AUC_{0-\infty}$ .
- $V_d$  (if measurable serum levels are obtained and an elimination rate constant ( $\lambda_z$ ) is estimable): Apparent volume of distribution at steady state of the drug will be determined from trough levels.

Serum concentration below LLOQ prior to dose for the assay will be set to zero for the PK analysis. For other cases concentrations below LLOQ will be set for non-informative missing. Exact procedure for imputation of data will be described in the SAP.

All samples obtained from all cohorts will be analyzed to avoid bias in data presentation.

Sparse sampling analysis may be used to mitigate the risk of insufficient data to create individual profiles.

Drug concentrations will be summarized by nominal time point if 3 or more values are available. Descriptive statistics for PK parameters will be performed if  $\geq 50\%$  of subjects have evaluable data and number of values to summarize is  $\geq 3$ .

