2.1 General Study Design

The first-in-human study of QR-110 will be an open-label, multiple arm, multiple dose, dose escalation study to evaluate the safety and tolerability of QR-110 administered via IVT injection in subjects with LCA due to the *CEP290* p.Cys998X mutation. Subjects will be assigned to receive a specified dose level (loading dose and maintenance dose) of QR-110. No intrasubject dose escalation is planned. Up to 3 dose levels of QR-110 will be evaluated. Dose escalation decisions and initiation of dosing in pediatric subjects (6 to < 18 years of age) will be determined by the Data Monitoring Committee (DMC) and Sponsor Medical Monitor review of safety and tolerability data. The DMC and Sponsor Medical Monitor will also review all available safety data at key study time points (e.g., prior to the first subject in the first adult cohort (Cohort A1) receiving each subsequent dose of study drug).

QR-110 will be administered by unilateral IVT injection. Each subject will receive up to 4 doses of QR-110 in their worse eye (as defined by visual acuity at the Screening Visit, subsequently referred to as treatment eye) every 3 months and will be assessed for safety and tolerability at follow-up visits. The worst eye or treatment eye is defined in Section 8.1 of the SAP.

No placebo nor sham injections will be administered in the contralateral eye. The contralateral eye and the subject's own baseline measurements will serve as controls.

The DMC and/or Sponsor Medical Monitor may decide to de-escalate the dose, hold the dose (delay or skip), or discontinue study drug for an individual subject, in consultation with the Investigator. Subjects who discontinue study drug will continue to be followed for safety and efficacy.

An extension study is planned but is not within the scope of this SAP.

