2.5 Schedule of Visits and Assessments

3. Study Treatments

In this multiple arm multiple dose escalation study QR-110 will be administered by unilateral IVT injection. Each subject will receive up to 4 doses of QR-110 in their worse eye (defined in Section 8.1 of the SAP) at least 3 months apart and will be assessed for safety and tolerability at follow-up visits. Up to 3 dose levels will be tested (loading dose/maintenance dose):

- Low Dose: One 160 µg loading dose, followed by up to three 80 µg maintenance doses
- Mid Dose: One 320 µg loading dose, followed by up to three 160 µg maintenance doses
- High Dose: One 500 µg loading dose, followed by up to three 270 µg maintenance doses

QR-110 Solution for IVT Injection, 10 mg/mL and diluent, will hereby be referred to as IVT injection.

As noted previously in Section 2.3, no subjects were treated at the high dose, therefore only the low dose and mid dose will be considered within the statistical TLFs for this study.

4. Sample Size and Power Considerations

This is a phase 1b/2 safety study designed to evaluate the safety, tolerability and PK of QR-110. The sample size is not based on power calculations. It is chosen based on clinical experience and considered to be adequate to fulfill the objectives of the study.

Twelve subjects are planned to be enrolled in the study. However, depending upon observed results, the DMC and Sponsor Medical Monitor may add subjects as indicated in Section 4.2.2.2 of the protocol, for a maximum number of subjects up to a total of n = 18.

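### The serum PK section labels apparent clearance as clearance and plans a steady-state volume from trough levels without a formula; both lines need rewording, with minor impact

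*SAP*

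**What the plan says.** Serum pharmacokinetics is a secondary objective (SAP section 1.2), and the matching endpoint in SAP section 1.5 is systemic exposure in serum.

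- **Route.** SAP section 2.1: "QR-110 will be administered by unilateral IVT injection". No intravenous arm is described and no value of F is given. Protocol section 2.4 says that "systemic absorption is anticipated to be low".
- **Clearance.** SAP section 13: "Serum clearance level will be estimated using the formula" CL = Dose/AUC0-inf. Protocol section 10.7 has the same formula: "Serum clearance will be estimated using the formula". Neither carries an F term or a /F label.
- **Volume.** SAP section 13: "Apparent volume of distribution at steady state of the drug will be determined from trough levels". Protocol section 10.7 and the synopsis say the same. No formula follows. The line applies only if serum levels are measurable and lambda-z can be estimated.
- **Doses.** Loading and maintenance doses differ twofold at both levels used, for example "Low Dose: One 160 µg loading dose, followed by up to three 80 µg maintenance doses" (SAP section 3). Protocol section 2.4: "Each subject will receive up to 4 doses of QR-110 at 3 month intervals". The CL formula does not say which dose is meant.
- **Reporting.** Geometric means and coefficients of variation of CL and Vd are planned for each dose group where possible.

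The protocol leaves exact PK details to a separate Pharmacokinetic Analysis Plan, which is not among the documents. SAP section 13 does not mention that plan, and the list of changes in SAP section 15 alters neither parameter.

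**The concern.** After an extravascular dose, serum AUC reflects only the fraction that reaches the circulation. Dose/AUC0-inf is then CL/F, and a reader of the report would take a value labelled clearance for the drug's true serum clearance.

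The volume line has a method problem. A serum trough after an intravitreal dose combines clearance, release from the eye, F and the dosing interval. A steady-state volume is CL times mean residence time, which needs intravenous data or a known input time and F. The word *apparent* covers the missing F, but it does not make a trough a source for a steady-state volume. Without a formula, two programmers could also follow the text and report very different numbers.

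A third point arises if the formulas are applied to doses 2 to 4. AUC extrapolated to infinity then includes drug left from earlier doses, while the numerator holds only the latest dose. At stake are two tabulated secondary PK parameters.

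**Working it through.** The plan gives formulas and no numerical result, so there is no figure to reproduce.

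**Inputs from the documents:** intravitreal route; low-level doses 160, 80, 80, 80 µg; interval tau = 3 months, taken as 90 days; CL = Dose/AUC0-inf.

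**Assumed, not in the documents:** linear one-compartment serum kinetics with first-order release from the eye; true CL = 100 L/day and V = 15 L; F from 0.3 to 1.0; ocular release half-life h of 7, 30, 60 or 90 days. Release is then much slower than serum elimination (CL/V = 6.67 per day), so lambda-z = ln 2/h.

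**1. Clearance, first dose.** AUC0-inf = F × Dose/CL, so Dose/AUC0-inf = CL/F. This needs only linear kinetics. Read as CL, it is 1/F times the truth: 1.00 (F = 1.0), 1.43 (0.7), 2.00 (0.5), 3.33 (0.3).

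**2. Volume, F = 1, trough at the end of the fourth interval.** Let r = 2^(−90/h), the fraction left in the eye after one interval. Three calculations:

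- A: Dose/trough = 80/C
- B: steady-state trough formula with lambda-z = 80 × [r/(1 − r)]/C
- Vz/F = Dose/(lambda-z × AUC0-inf) = 100 × h/ln 2, from the first dose

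| h (days) | A (L) | B (L) | Vz/F (L) |
|---|---|---|---|
| 7 | about 7.4 million | 995 | 1,010 |
| 30 | 30,100 | 4,310 | 4,328 |
| 60 | 15,600 | 8,530 | 8,656 |
| 90 | 13,000 | 13,000 | 12,984 |

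Example at h = 30: r = 0.125 and C = 0.00265 µg/L. Then A = 80/0.00265, about 30,100 L, and B = 80 × (0.125/0.875)/0.00265, about 4,310 L.

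A exceeds B by the factor (1 − r)/r = 2^(tau/h) − 1, which is 7 at h = 30 and 1 at h = 90. Reading A therefore moves with the dosing interval. Reading B stays within about 2% of Vz/F. None of the three approaches the assumed V of 15 L, because with slow release they all reflect the release rate.

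**3. Carry-over at dose 4.** The amount in the eye just after dose 4 is A4 = 80 + 80r + 80r² + 160r³, and AUC0-inf from then on is F × A4/CL. The plan's formula returns 80/A4 times CL/F:

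- h = 7: 80/80.01 = 1.00
- h = 30: 80/91.56 = 0.87
- h = 60: 80/125.36 = 0.64
- h = 90: 80/160 = 0.50

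**4. Does AUC over the interval repair this?** It replaces A4 by A4 × (1 − r). At dose 4 the ratios become 1.00, 1.00 (80/80.12), 0.99 (80/81.04) and 1.00. At dose 2, with A2 = 80 + 160r, they are 1.00, 0.91 (80/87.5), 0.91 (80/88.28) and 1.00. The repair works near steady state and is less exact at dose 2.

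**The case against.** The best defence of the volume line is that its lambda-z condition would serve no purpose if Dose/trough were meant. It points to a trough-plus-lambda-z calculation, which gives nearly the same number as the conventional Vz/F. This stands. A reader might infer that any trough-based volume must be out by a large multiple; the documents do not support that, because they state no formula and no half-life. What remains is that the formula is missing and the result is not a steady-state volume. Vz/F is no clean substitute either: when release is rate-limiting it also reflects release from the eye.

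A reader might also infer that Vd cannot be computed at all, since "Serum concentration below LLOQ prior to dose for the assay will be set to zero for the PK analysis". That depends on whether the rule covers pre-dose samples at doses 2 to 4 or only the first. Other values below the limit are set to half of it, and Vd is attempted only when levels are measurable.

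The carry-over point is conditional too. The PK sampling schedule is not in the available text, and the statement that parameters are calculated for each dose may mean each dose level.

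Finally, the Pharmacokinetic Analysis Plan may already hold correct formulas. That cannot be checked. The SAP says that its methods supersede the protocol's, so its own text should be right.

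**Conclusion.** The point holds as a labelling and specification fault of minor consequence. For a first dose under linear kinetics, Dose/AUC0-inf is CL/F whatever F is. The number is valid once relabelled, so calling the calculation itself wrong would go too far. The volume line is a method fault: a steady-state volume does not follow from serum troughs after intravitreal dosing, and without a formula the value depends on the reading. If the CL formula is applied to later doses, it understates CL/F: at dose 4 by nothing at a 7-day release half-life, rising to half at 90 days.

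All the volume and carry-over figures are illustrative, since they rest on the assumed model, half-lives, CL and V. The exposure measures Cmax, Tmax and AUC0-tlast are untouched, and dose escalation rests on safety and tolerability. Low systemic levels may also leave CL and Vd uncalculated, because summaries require at least three values and at least half of subjects evaluable.

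**What to change.** In SAP section 13 and the Pharmacokinetic Analysis Plan:

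1. Relabel CL as CL/F.
2. Replace the Vd line with Vz/F = Dose/(lambda-z × AUC0-inf), described as a terminal-phase apparent volume that also reflects ocular release if release is rate-limiting. Otherwise drop Vd.
3. State that Dose is the dose actually given, loading or maintenance.
4. Compute both for the first dose only. For later doses, use AUC over the dosing interval in place of AUC0-inf, if concentrations are near steady state.
5. List the change in SAP section 15, since protocol section 10.7 and the synopsis carry the present wording.

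The cost is a few lines of text. No new samples or data are needed.
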